4.1. Inclusion Criteria

Patients must meet all of the following inclusion criteria to be eligible for enrollment into the study:

1. Portion A: Histological diagnosis of advanced solid tumor malignancy or B-cell lymphoma, for which no curative therapy is available. For patients to be enrolled in the expansion cohorts:
 - Diagnosis of melanoma, renal cell carcinoma (RCC), non-small cell lung carcinoma (NSCLC), or squamous cell carcinoma of the head and neck (SCCHN);
 - Documented disease progression per RECIST v1.1 on a previous systemic immune checkpoint inhibitor therapy (anti-CTLA-4, anti-PD-1/PD-L1) administered as a single agent OR in combination;

- Measurable disease with at least 1 target lesion by RECIST v1.1 that has not been previously irradiated.
2. Portion B: Histological diagnosis of relapsed or refractory CD20-positive NHL for which no curative therapy is available, including small lymphocytic lymphoma (SLL)/chronic lymphocytic leukemia (CLL) with nodal disease (not including SLL/CLL with $>10,000$ lymphocytes/ μL , prolymphocytic leukemia, hairy cell leukemia, heavy chain disease, plasma cell myeloma, solitary plasmacytoma of bone, extraosseous plasmacytoma, lymphomatoid granulomatosis, and large B-cell lymphoma arising in Castleman disease). For patients to be enrolled in the expansion cohorts:
- Diagnosis of FL or DLBCL;
 - Measurable disease with at least 1 extranodal tumor mass >1.0 cm in the greatest transverse diameter (GTD) or in the case of malignant lymph nodes >1.5 cm in the GTD and the product of the diameters ≥ 2.25 cm² as measured by Computerized Tomography (CT) or Magnetic Resonance Imaging (MRI);
 - FL disease (Grade 1, 2, or 3a) refractory to rituximab defined as:
 - Lack of a CR or PR during a previous rituximab containing regimen comprising at least 2 doses of 375 mg/m², OR
 - Occurrence of PD within 6 months of completion of a previous rituximab containing regimen comprising at least 2 doses of 375 mg/m²
 - Treatment with ≥ 2 prior regimens for FL.
3. Availability of an archival (tissue collected within the last 6 months) OR baseline tumor biopsy (tissue collected *de novo* during the screening period); this tissue sample must be available also for a central pathology laboratory for independent review.
4. Age 18 years or older (or ≥ 20 years of age if required by local regulation).
5. Eastern Cooperative Oncology Group (ECOG) performance status of ≤ 1 .

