Appendix 3. Determination of Efficacy – Non-Hodgkin’s Lymphoma

Efficacy will be assessed using the International Working Group response criteria (Cheson Criteria Version 2007). Tumor responses are determined using information from objective measurements from CT scans, as well as clinical information including B-symptom evaluation, physical examination, ECOG performance status, assessment of liver and spleen, laboratory assessments such as bone marrow biopsies and/or aspirates, biochemical markers of disease activity (ie, LDH) and hematology results.

Tumor and clinical assessments will be performed as described in the Tumor Assessment flowchart. Treatment delays should not alter the schedule of tumor and clinical assessment evaluations and should continue at the frequency outlined in the flowchart.

For patients to be considered evaluable for efficacy, they must have completed at least 1 follow-up radiological tumor assessment post randomization, they must have received sufficient investigational product (at least one cycle of PF-05082566) and they must not have had any major protocol violations as determined by the sponsor.

Measurable/Abnormal Lesions

A nodal site of disease is considered measurable/abnormal if:

- Any nodal lesion can have a single diameter of >15 mm in the GTD, and the perpendicular dimension to the GTD must have a diameter >10 mm in order to be considered abnormal and measurable.
- Any nodal lesion can have >10 mm through ≤15 mm in the GTD, and the perpendicular dimension to the GTD must have a diameter >10 mm to be considered abnormal.

A nonnodal site of disease is considered measurable/abnormal if it measures ≥10 mm in 2 perpendicular dimensions.

Nonmeasurable Lesions

All non nodal sites of disease that that measure <10 mm in a single GTD are considered non measurable. Other sites of disease that are considered evaluable, but not measurable include pleural effusions, ascites and bone lesions.

Index Lesions

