Up to 6 measurable/abnormal lesions should be selected as index lesions. Lesions can be selected as index lesions if they are clearly measurable in 2 perpendicular dimensions. Lesions cannot be selected as index lesions if they have been in an area of prior radiotherapy without evidence of progression. These lesions should be selected from disparate regions of the body as possible and should include mediastinal and retroperitoneal sites if these sites are involved. The greatest transverse diameter and the greatest perpendicular transverse diameter will be recorded for each index lesion. The product of these 2 dimensions will be recorded and the sum of the product diameters (SPD) of the index lesions will be the baseline value used in determining response.

Non-Index Lesions

All other lesions, either measurable or non measurable, are considered non index lesions. Multiple lesions may be grouped together as a non-index lesion (ie, multiple bony lesions in scapula). The status of the non index lesion will be recorded on the CRF.

Method of Measurement

- At a minimum, conventional CT or MRI should be performed with contiguous slices of 10 mm or less in thickness. Spiral CT should be performed by use of 8 mm or less contiguous reconstruction interval. The same method of measurement should be used throughout.
- CT scans with contrast should be performed for radiographic assessments. If a chest CT is not feasible with contrast, a non contrast CT should be performed. If CT abdomen/pelvis with contrast is not feasible, then an MRI of the abdomen/pelvis should be performed.
- Positron emission tomography (PET) scans should not be used for the determination of response, however, may be obtained if clinically indicated. Additionally, ultrasounds should not be used for purposes of measuring or evaluating disease in this study.

Clinical Assessments

In addition to radiographic tumor measurements, other clinical assessments should be obtained when evaluating disease. These include:

- Physical examination findings, evaluation presence, absence or any new lymph nodes. Additionally, an assessment of ECOG performance status will be obtained.
- Evaluation of B-symptoms.
- Bone marrow biopsies and/or aspirates.
- Evaluation of the liver and spleen.
- Biochemical markers of disease, including LDH.

Response Criteria

Evaluation of Index Lesions

Term	Definition

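### Portion B entry and Appendix 3 define measurable disease differently, so an eligible patient can have no index lesion, cannot be scored PR, and is a non-responder in the primary ORR unless CR is recorded

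*Protocol*

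**What the plan says.** **Entry (Protocol Section 4.1, criterion 2, expansion cohorts).** A patient qualifies with "Measurable disease with at least 1 extranodal tumor mass >1.0 cm in the greatest transverse diameter (GTD"), or with a malignant node above 1.5 cm in GTD "and the product of the diameters ≥ 2.25 cm² as measured by" CT or MRI. The extranodal limb limits one diameter only. The nodal limb has a product but no separate limit on the shorter diameter. Neither limb mentions earlier irradiation. In Portion A, criterion 1 does require a target lesion that has not been irradiated.

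**Assessment (Protocol Appendix 3).** "A nonnodal site of disease is considered measurable/abnormal if it measures ≥10 mm in 2 perpendicular dimensions". For nodes above 15 mm in GTD, "the perpendicular dimension to the GTD must have a diameter >10 mm in order to be considered abnormal and measurable". Index lesions are chosen from measurable/abnormal lesions, and "Lesions cannot be selected as index lesions if they have been in an area of prior radiotherapy without evidence of progression". Every other lesion is non-index.

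**Scoring.** In Appendix 3, PR needs a fall of at least 50% in the summed diameter products (SPD) of the index lesions. CR is worded as disappearance of all detectable disease and needs no SPD. The Overall Response table has a not-applicable entry for patients without non-index lesions, but none for patients without index lesions.

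**Analysis (SAP Sections 4.1, 6.2.2 and 6.2.2.1).** Portion B is non-randomized, so the full analysis set (FAS) is every dosed patient. ORR is the share of that set with CR or PR. Best overall response is built from the reported overall responses. For solid tumors the SAP has a non-CR/non-PD category for non-measurable disease; for NHL it has none.

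**The concern.** Objective response by Cheson 2007 is the primary endpoint of the Portion B expansion cohorts. If the entry rule admits a patient whom the assessment rule cannot measure, a true partial response in that patient has no way of being counted, while the patient stays in the denominator. The bias runs one way, downward.

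The result would also depend on how each site handles a case that the plan leaves open. Images from the refractory FL patients go to a central laboratory for possible independent review (Table 5, tumor assessment footnote), and a central reader could resolve the same case differently. The SAP's NHL waterfall plot is limited to patients with measurable disease at baseline, a term with two meanings here. Finally, efficacy in FL-1 and FL-2, with up to 20 patients each, feeds the dose choice for FL-3 (Protocol Section 3.1.2), and one patient weighs more there than among 80.

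**Working it through.** **1. The plan's own figures.** Protocol Section 9.3 gives Clopper-Pearson intervals at n = 80. Recomputed from beta quantiles: 40/80 gives 38.6 to 61.4%, 44/80 gives 43.5 to 66.2%, 48/80 gives 48.4 to 70.8%, and 56/80 gives 58.7 to 79.7%. All four agree with the plan. The maximum standard error is √(0.25/80) = 0.056, stated as 0.06. The arithmetic is sound; the question is who can become a responder.

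**2. The two definitions, lesion by lesion.**

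| Lesion (mm) | Product (cm²) | Entry, criterion 2 | Appendix 3 |
|---|---|---|---|
| Node 26 × 9 | 2.34 | met | not met (9 is not above 10) |
| Node 25 × 9 | 2.25 | met | not met |
| Node 23 × 10 | 2.30 | met | not met (10 is not above 10) |
| Extranodal 30 × 8 | 2.40 | met | not met (8 is below 10) |
| Node 16 × 14 | 2.24 | not met | met |

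For nodes in general, a perpendicular of at most 10 mm with a product of at least 225 mm² needs a GTD of at least 225/10 = 22.5 mm. Elongated nodes of that length or more can fall in the gap.

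**3. The irradiation gap.** This one does not depend on size. Criterion 2 counts FL as refractory if there was no CR or PR on a rituximab regimen, which does not require progression. Exclusion criterion 8 bars only radiotherapy in the previous 14 days. So a patient whose only qualifying node lies in an older field and has not progressed can be eligible, yet Appendix 3 bars that node as an index lesion.

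**4. Following such a patient through the scoring.** With no index lesion there is no baseline SPD, so a 50% fall is undefined and PR cannot be derived. Non-index lesions can be scored CR, but every CR row of the Overall Response table also needs an index-lesion CR. PD can still be reached through the rows that accept any index status. The SAP keeps the patient in the FAS as a non-responder unless a CR is reported.

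**5. Size.** Let π be the true ORR, n the number of patients, and k the number without an index lesion. If none of the k can be counted as a responder:

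expected ORR = π(n − k)/n

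The documents do not give k. The values below are assumptions, with π = 50%.

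- n = 80, k = 2: 0.5 × 78/80 = 48.8%
- n = 80, k = 4: 0.5 × 76/80 = 47.5%
- n = 80, k = 8: 0.5 × 72/80 = 45.0% (36/80, interval 33.8 to 56.5%)
- n = 20, k = 1: 0.5 × 19/20 = 47.5%
- n = 20, k = 2: 0.5 × 18/20 = 45.0%

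These are worst cases. If a share c of the responses among the k patients are complete and recorded as CR, then expected ORR = π(n − k + ck)/n. Protocol Section 1.4 reports 4 CRs among 8 FL responders. Taking c = 0.5 from that, purely as an illustration, n = 80 gives 0.5 × 79/80 = 49.4%, 0.5 × 78/80 = 48.8% and 0.5 × 76/80 = 47.5% for k = 2, 4 and 8. The loss is halved.

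**The case against.** The strongest reply is that the case is rare and small. It arises only when no other lesion qualifies. Appendix 3 allows up to six index lesions and bars irradiated ones only if they have not progressed. Even k = 8 moves the estimate by 5 points against an interval of 38.6 to 61.4% for 40/80, and no hypothesis is tested. Counting unscored patients as non-responders is prespecified and conservative, and the SAP tabulates the reasons for a not-evaluable best response. All of this stands and limits the size of the point. It does not supply the missing scoring rule.

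The extranodal example is also arguable. Appendix 3 says that lesions clearly measurable in two perpendicular dimensions can be index lesions, and it calls a non-nodal site non-measurable only below 10 mm in GTD. A 30 × 8 mm mass falls in neither class, and a site might select it. The nodal and irradiation examples do not depend on this.

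Part of Protocol Section 7 is redacted, including Section 7.7 on tumor response, so a rule for this case may exist there. The visible criterion 2 and Appendix 3 would still disagree.

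Three stronger readings are tempting, and the documents support none of them:

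- **That such a patient can never be scored CR.** The CR wording needs no SPD, the SAP uses reported overall responses, and one documented CR is enough for NHL.
- **That the overall response is always unable-to-evaluate.** PD remains reachable. That category describes missing or unassessed index lesions, which presupposes that there are some. The case is undefined rather than assigned.
- **That patients such as one with a 16 × 14 mm node are wrongly turned away.** An entry threshold stricter than the measurement threshold is a legitimate choice.

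**Conclusion.** The point holds in a limited form. The two definitions conflict, and a patient can be eligible with no index lesion. PR is then not derivable, the Overall Response table shows no route to CR, and the patient lowers the primary ORR unless the investigator records CR.

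The number of such patients is unknown and probably low. At a true ORR of 50% and n = 80, the worst-case loss is 1.2, 2.5 or 5.0 points for an assumed 2, 4 or 8 patients, and less if CRs are recorded. In a cohort of 20, one patient costs up to 2.5 points in expectation. None of this invalidates the endpoint. It leaves a primary-endpoint outcome to each site's interpretation, which wording can prevent. The conclusion rests on the visible text and on reading the product rule as belonging to the nodal limb; the 30 × 8 mm example passes entry on either reading.

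**What to change.** 1. Use one definition. Either criterion 2 requires at least one lesion that qualifies as an index lesion under Appendix 3, including the irradiation condition, or Appendix 3 adopts the entry definition. The two passages must be reconciled.
2. Add a row to the Appendix 3 Overall Response table for patients without index lesions, and a matching rule for NHL in SAP Section 6.2.2.1.
3. For patients already enrolled, have the SAP list those with no Appendix 3 index lesion and report ORR with and without them, keeping the FAS as the primary set.

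The cost is wording in the next amendment, one SAP rule, and one listing with a sensitivity estimate. Changing criterion 2 would shift eligibility slightly at the margin. No new data are needed beyond the baseline lesion diameters that Appendix 3 already records and the earlier radiotherapy fields, assuming the prior-radiation CRF page identifies the site.

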As of June 2016, the highest planned dose of 10 mg/kg PF-05082566 in combination with rituximab was tested with no DLTs reported in Portion B and no further dose escalation was performed. As of September 2016, 10 patients with rituximab-refractory FL (see [Section 4.1](#) for definition of FL disease refractory to rituximab) and 4 patients with relapsed or refractory DLBCL have been enrolled in the expansion cohort of Portion B and treated at the 1.2 mg/kg dose level of PF-05082566. Because the RP2D of PF-05082566 administered in combination with rituximab has not yet been determined in Portion B, enrollment will be expanded to enroll up to 100 patients with rituximab-refractory FL. Patients with rituximab-refractory FL will be treated with rituximab in combination with PF-05082566 at the 1.2 mg/kg and, following an assessment of the tolerability, efficacy **CCI** and PK data collected for the combination of PF-05082566 at 1.2 mg/kg plus rituximab, at the 0.24 mg/kg dose level. In the first cohort (FL-1), up to 20 patients will be treated with rituximab in combination with PF-05082566 at 1.2 mg/kg and in the second cohort (FL-2) up to 20 patients may receive rituximab in combination with PF-05082566 at 0.24 mg/kg. The PF-05082566 dose level to be administered in the third cohort (FL-3) will be selected based on the overall evaluation of tolerability, efficacy **CCI** and PK data collected for the combination of PF-05082566 plus rituximab in FL-1 and FL-2 (if this cohort is enrolled). In FL-3, approximately 60 patients will receive rituximab in combination with PF-05082566 either at the 0.24 or 1.2 mg/kg dose level.

The objective of the expansion cohorts is to provide additional safety, tolerability, PK **CCI** and preliminary efficacy data for PF-05082566 in combination with rituximab, in order to support the selection of the RP2D. **CCI**

Cumulative safety data will continue to be evaluated using the Bayesian statistical model. Should emerging data indicate that any of the dose levels tested in the expansion cohort is more toxic than previously estimated (>25% DLT rate), **CCI** and may be declared as the RP2D for PF-05082566 in combination with rituximab.

Japanese sites are currently participating in Portion B following the evaluation of the PF-05082566 safety profile in Japanese patients enrolled in Portion A.

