3.4. DLT Definition

Severity of AEs will be graded according to CTCAE v 4.03. AEs meeting the following definition occurring in the first two cycles of treatment (up to 28 days post second dose) which are not related to progressive disease and attributable to PF-05082566 alone (Portion A) or to PF-05082566 in combination with rituximab (Portion B) will be classified as DLTs:

Hematologic:

- Grade 4 neutropenia [absolute neutrophil count (ANC) $<500/\text{mm}^3$ or $<0.5 \times 10^9/\text{L}$] lasting >7 days;
- Febrile neutropenia (defined as neutropenia \geq Grade 3 [ANC $<1000 \text{ cells}/\text{mm}^3$] and a body temperature $\geq 38.5^\circ\text{C}$);
- Neutropenic infection (ANC $<1,000/\text{mm}^3$ or $<1.0 \times 10^9/\text{L}$, and Grade >3 infection);
- Grade ≥ 3 thrombocytopenia ($<50,000 - 25,000/\text{mm}^3$ or $<50.0 - 25.0 \times 10^9/\text{L}$) with bleeding;
- Grade 4 thrombocytopenia ($<25,000/\text{mm}^3$ or $<25.0 \times 10^9/\text{L}$) >3 days;
- Grade 4 anemia (hemoglobin $<6.5 \text{ g/dL}$ or 4.0 nmol/L);
- Grade ≥ 3 hemolysis ($>2 \text{ gm}$ decrease in hemoglobin requiring medical intervention [transfusion or steroids]).

Non-Hematologic:

- Grade ≥ 3 toxicities, except those grade 3 events that respond to treatment (eg, grade 3 nausea, vomiting, diarrhea that responds to standard medical supportive care within 48 hours would not be considered a DLT).

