6. Adequate bone marrow function, for Portion A defined as absolute neutrophil count (ANC) $\geq 1.5 \times 10^9/\text{L}$ ($\geq 1,500/\mu\text{L}$), platelet count $\geq 100 \times 10^9/\text{L}$ ($\geq 100,000/\mu\text{L}$), and hemoglobin >9.0 g/dL (>5.6 mmol/L), and for Portion B as ANC $\geq 1.0 \times 10^9/\text{L}$ ($\geq 1,000/\mu\text{L}$), platelet count $\geq 75 \times 10^9/\text{L}$ ($\geq 75,000/\mu\text{L}$), and hemoglobin ≥ 8.0 g/dL (≥ 5.0 mmol/L) or ≥ 8.5 mmol/L (≥ 5.3 mmol/L) for Japanese patients. In both cases, patients must be transfusion independent [ie, no blood product transfusions for a period of at least 14 days prior to enrollment (Portion B) or randomization (Portion A)].

7. Adequate Renal Function, including serum creatinine ≤ 2 x upper limit of normal (ULN) or estimated creatinine clearance ≥ 50 mL/min as calculated using the method standard for the institution.
8. Adequate Liver Function, including: a) Total serum bilirubin ≤ 1.5 x ULN unless the patient has documented Gilbert syndrome; b) Aspartate and Alanine Aminotransferase (AST and ALT) ≤ 2.5 x ULN.
9. Adequate Cardiac Function, as measured by left ventricular ejection fraction (LVEF) that is greater than 40%, or the presence of New York Heart Association (NYHA) classification of no greater than stage II congestive heart failure.
10. Resolved acute effects of any prior therapy to baseline severity or Grade ≤ 1 CTCAE v. 4.03 except for AEs not constituting a safety risk by investigator judgment.
11. Serum or urine pregnancy test (for females of childbearing potential) negative at screening. Female patients of nonchildbearing potential must meet at least 1 of the following criteria:
 - Achieved postmenopausal status, defined as follows: cessation of regular menses for at least 12 consecutive months with no alternative pathological or physiological cause;
 - Have undergone a documented hysterectomy and/or bilateral oophorectomy;
 - Have medically confirmed ovarian failure.All other female patients (including female patients with tubal ligations) are considered to be of childbearing potential.
12. Male and female patients of childbearing potential and at risk for pregnancy must agree to use two highly effective method(s) of contraception throughout the study and for at least 90 days (180 days if required by local regulation) after the last dose of assigned treatment.

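### Inclusion criterion 6 prints the Portion B hemoglobin limit for Japanese patients as two different figures in the same unit (8.5 and 5.3 mmol/L), so it cannot be applied as written.

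*Protocol*

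**What the plan says.** Criterion 6 in Protocol Section 4.1 contains three hemoglobin limits.

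- **Portion A:** above 9.0 g/dL, with the SI equivalent in brackets; the text runs "5.6 mmol/L), and for Portion B as ANC".
- **Portion B, general:** at least 8.0 g/dL, with at least 5.0 mmol/L in brackets.
- **Portion B, Japanese patients:** at least 8.5 mmol/L, with a bracketed second figure, "5.3 mmol/L) for Japanese patients. In both cases, patients must be transfusion independent".

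The first two limits give g/dL and then mmol/L. Only the third gives mmol/L twice, with different numbers.

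The limit is in current use. Section 3.3.2 states: "Japanese sites are currently participating in Portion B following the evaluation of the PF-05082566 safety profile". Section 3.3.1.1 also has Japanese sites in the expansion cohorts. Section 3.1.2 plans up to 100 rituximab-refractory FL patients, of whom 10 had been enrolled by September 2016.

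Section 3.4 has a related slip: Grade 4 anemia, as a DLT, is given as hemoglobin below 6.5 g/dL, with 4.0 nmol/L as the alternative.

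**The concern.** Section 4.1 requires every inclusion criterion to be met, so criterion 6 decides who may enter. For Japanese patients it offers two limits that are far apart. If the first figure governs, patients are turned away at hemoglobin values well above the limit for everyone else in Portion B. If the bracketed figure governs, the same patients fail a limit printed in the protocol. Under SAP Section 6.5.2.2, patients dosed without satisfying the inclusion criteria are reportable deviations, so whether such a patient counts as a deviation depends on which figure the reader picks.

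The scope is also unclear. Criterion 6 does not say whether Japanese patients are those enrolled in Japan or Japanese patients at any site. Criteria 4 and 12 attach their local exceptions to local regulation; criterion 6 attaches its exception to neither a country nor a regulation.

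**Working it through.** **Inputs, all from criterion 6:** 9.0 g/dL with 5.6 mmol/L; 8.0 g/dL with 5.0 mmol/L; 8.5 mmol/L with 5.3 mmol/L.

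**Formula:** mmol/L = k × g/dL. The documents state no value of k, so it is inferred from the two pairs whose units differ.

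**Step 1. Recover k and check that the two clean pairs agree.**
- Portion A pair: k = 5.6 / 9.0 = 0.622.
- General Portion B pair: k = 5.0 / 8.0 = 0.625.
- Allowing for rounding of the bracketed figures to one decimal, the pairs permit k from 4.95 / 8.0 = 0.619 to 5.65 / 9.0 = 0.628.
- The usual factor, about 0.6206, lies inside that range. It is an outside assumption and serves only as a cross-check: 0.6206 × 9.0 = 5.59 and 0.6206 × 8.0 = 4.96, which round to the printed 5.6 and 5.0.

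**Step 2. Convert the Japanese pair as printed.**

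| k | 8.5 mmol/L in g/dL | 5.3 mmol/L in g/dL | Gap (g/dL) |
|---|---|---|---|
| 0.622 (5.6/9.0) | 13.66 | 8.52 | 5.14 |
| 0.625 (5.0/8.0) | 13.60 | 8.48 | 5.12 |
| 0.6206 (assumed) | 13.70 | 8.54 | 5.16 |

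Over the full rounding range of k, 8.5 mmol/L lies between 13.5 and 13.7 g/dL. The two printed figures differ by a factor of 8.5 / 5.3 = 1.60, whatever k is.

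**Step 3. Read off the consequence.**
- Below about 8.5 g/dL, a Japanese patient fails both figures.
- At or above about 13.6 to 13.7 g/dL, the patient meets both.
- In between, the patient meets the bracketed figure and fails the first.

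The first figure is about 1.7 times the general Portion B limit (13.6 / 8.0 = 1.70).

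**Step 4. Test the simplest explanation.** Suppose the 8.5 was meant in g/dL, like the lead figures of the other two pairs. Then 8.5 × 0.622 = 5.29, 8.5 × 0.625 = 5.31 and 8.5 × 0.6206 = 5.27. All round to the printed 5.3. This fits a unit misprint but does not prove what was intended.

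**Section 3.4, for completeness.** 6.5 × 0.622 = 4.04, so 6.5 g/dL is about 4.0 mmol/L. Beside it stands 4.0 nmol/L, a unit one million times smaller.

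**The case against.** The strongest reply is that the text decodes itself. The other two limits run g/dL then mmol/L, and reading the first Japanese figure as g/dL gives the bracketed 5.3 to one decimal. A floor near 13.7 g/dL would look odd to any site in a criterion that admits other patients at 8.0 g/dL. That is fair, and it makes a misprint the likely explanation. It does not settle the matter: this is an entry criterion, and there is no second statement of the Japanese limit to check it against.

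A reader might go further and infer that the protocol excludes Japanese patients below 13.7 g/dL. The documents do not support this. It follows only if the first figure governs and the bracket is ignored; read in full, the criterion is contradictory rather than restrictive.

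A reader might also expect sites to settle on different limits and stay apart. In the non-randomized cohorts, Section 5.1.2 requires a registration form and the sponsor's written confirmation before dosing. The section does not say that hemoglobin is rechecked, but one central step makes lasting divergence less likely. The documents contain no eligibility checklist, so nothing shows which figure sites use.

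Finally, a reader might infer that the Section 3.4 unit distorts the dose-toxicity model. That is not supported. The g/dL figure leads, nobody could apply a nanomolar hemoglobin limit, and a one-letter difference may be a slip in reading the PDF.

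**Conclusion.** Wrong as written. Criterion 6 gives one limit as two figures in one unit, about 13.6 to 13.7 g/dL and about 8.5 g/dL, and a Japanese patient between them both meets and fails it. The contradiction itself rests on no assumption about conversion; the g/dL values rest on the factor implied by the criterion's own pairs and barely move over the range those pairs allow.

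The evidence favours a unit misprint in the first figure, but the documents do not confirm the intended limit. How many patients are affected cannot be stated, because the documents give neither the number of Japanese patients expected in Portion B nor their hemoglobin distribution. The fault is confined to eligibility: no sample size, confidence interval, response definition or analysis changes. The Section 3.4 unit is an editorial matter and adds no weight.

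**What to change.** - The sponsor should confirm the intended Portion B hemoglobin limit for Japanese patients and restate criterion 6 so that both figures express that one quantity, in the g/dL (mmol/L) form used for the other limits.
- The criterion should say whether the limit applies to patients enrolled in Japan or to Japanese patients at any site.
- As an editorial note, the two units in the Section 3.4 Grade 4 anemia criterion should be reconciled.

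The cost is a few words in the protocol, carried through to any site material that repeats the criterion. If Japanese patients have already entered Portion B, the sponsor should also record which figure was applied to them, so that deviations under SAP Section 6.5.2.2 are judged against one limit.
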